7. DRUG FORMULATION AND ADMINISTRATION

7.1 Description

GVAX is a vaccine composed of cells from lethally irradiated, autologous colorectal or hepatic metastasis engineered by adenoviral mediated gene transfer to secrete GM-CSF

7.2 Form

Cells will be thawed in a dedicated laminar flow biosafety cabinet in the CMCF and washed. Cells will be resuspended in a volume of 1 ml. of sterile saline for administration.

7.3 Storage and Stability

Tumor cells for vaccination and immunologic evaluation will be cryopreserved and stored in liquid nitrogen. A minimum of six individual vaccine aliquots will be prepared for each patient. Cell dose per aliquot will be fixed for an individual patient and will range from a minimum of 1×10^5 cells per aliquot to 1×10^7 cells per aliquot. The dosage will be determined by dividing the total cell yield following transduction into six aliquots (after QC removal). Thus, a minimum of 6.5×10^5 cells total will be required to prepare six aliquots of 1×10^5 cells. For total cell yields greater than 6×10^7 cells total, individual aliquots will remain at 1×10^7 cells per dose.

7.4 Handling

Qualified personnel, familiar with procedures that minimize undue exposure to themselves and the environment, should undertake the preparation, handling, and safe disposal of the chemotherapeutic agent in a self-contained and protective environment.

7.5 Availability

GVAX is an investigational agent and will be supplied free-of-charge from CMCF.

7.6 Preparation

Tissue obtained from a patient by hepatic resection will transferred to the Cell Manipulation Core Facility (CMCF) at the Dana Farber Cancer Institute in a sterile container containing sterile media. The tissue will be processed to single cell suspension by mechanical and enzymatic digestion as required; short-term tumor cultures may be established if necessary. Tumor cells will be transduced with a replication defective adenoviral vector encoding human GM-CSF.

After transduction, the tumor cells will be washed extensively and irradiated with 10,000 cGy.

A small aliquot of the transduced cells will be placed into culture and GM-CSF secretion will be determined by ELISA. The target level for GM-CSF production will be at least 40 ng/ 10^6 cells/24 hours, although achieving this secretion will not

be required for vaccine administration. Routine sterility cultures and testing for endotoxin and mycoplasma contamination will be performed.

Individual vaccine cell dose will vary depending on the final cell yield from vaccine production. The total cell yield will be divided in 6 aliquots, and the minimal dose will be 1×10^5 cells/vaccine and maximal dose will be 1×10^7 cells/vaccine. This variation in cell dosage is designed to maximize each patient's opportunity of receiving vaccinations and is not based on any expectation of significant differences in toxicity as a function of cell number.

7.7 Administration

Vaccinations will be administered on days 1, 8, 15, and every two weeks thereafter until 6 vaccines have been administered or the patient is removed from study.

Individual vaccine cell dose will vary depending on the final cell yield from vaccine production. The total cell yield will be divided in 6 aliquots, and the minimal dose will be 1×10^5 cells/vaccine and maximal dose will be 1×10^7 cells/vaccine. Cells will be thawed in a dedicated laminar flow biosafety cabinet at CMCF and washed. Cells will be resuspended in a volume of 1 ml. for administration. 2 injections (1/2 dose subcutaneously and 1/2 dose intradermally) will be given and will constitute a single vaccination. The volume of each injection will be 0.5 ml.

A study team physician, PA, NP or RN will administer the injections. Injections will be administered in the outpatient setting according to standard procedure in the patient's arms and thighs on a rotating basis.

7.8 Ordering

The vaccine will be manufactured at the Cell Manipulation Core Facility, (CMCF). Once an Order for Processing has been received by CMCF, cells will be thawed for administration.

7.9 Accountability

Study reagent accountability is maintained by the Cell Manipulation Core Facility (CMCF).

7.10 Destruction and Return

CMCF will receive reagents. If they are not used the reagents will be held for future use until they are out of date at which point they will be destroyed according to institutional policies. Destruction will be documented in the Drug Accountability Record Form.

8. CORRELATIVE/SPECIAL STUDIES

Immunoologic studies will be performed on peripheral blood at designated time points as well as the resected hepatic metastasis and skin punch biopsies. Punch skin biopsies will be obtained 2 days after the first and fifth vaccinations. A piece of the resected hepatic metastasis will be fresh frozen and stored at -80 degrees at MGH. The remainder of the specimen will be stored in paraffin at MGH. If the patient had a colorectal resection at MGH in the past we may analyze the immune infiltrate of the primary cancer which is banked in paraffin (see 8.1.3); however, resection of the primary tumor at a hospital other than MGH is not an exclusion criterion.

If the patient develops recurrent disease, and undergoes clinically indicated resection, biopsies may also be obtained for immune analysis as well.

- 8.1.1 Vaccine site reactions: Punch skin biopsies will be obtained 2 days after the first and fifth vaccinations. Histological analysis for macrophages, dendritic cells, eosinophils, and lymphocytes will be performed as a research test. Specimen's will be transported in 10% formalin to the CMCF where they will be logged in for research.
- 8.1.2 Tumor infiltrates: The primary and hepatic lesions will be scored, as a research test, for cellular infiltrates (CD8+ T cells, CD4+ T cells, Treg, macrophages, etc), inflammation, edema, fibrosis, and percentage tumor cell death. Ten high power fields will be evaluated and the numbers summed. The character and type of infiltrating cells will be evaluated by routine histological and appropriate immunohistochemical analysis. Attempts will be made to obtain discarded tissue from biopsies performed to document disease recurrence as part of the patients' standard of care. The discarded tissue from the recurrent disease biopsies will also be assessed for immune infiltrates as part of the correlative science in this protocol.
- 8.1.3 Blood analyses: Serum and circulating mononuclear cells will be frozen prior to beginning vaccination and at regular intervals thereafter as described in Section 9.0. These samples will be used in research studies aimed at identifying the target antigens of vaccination. We may also use these samples, in research tests to measure immune responses against adenoviral proteins expressed in the vector used for vaccine preparation.

9.0 STUDY CALENDAR

Data Collection

Test	Day -21*	Day 1	Days 8, 15	Days 29, 43, 57	Restage ¹	Additional Vaccines
History/PE	X	X	X	X	X	
Weight/VS	X	X ⁹	X	X	X	X
CBC with Diff	X	X	X	X	X	X
PT, PTT	X					X ⁷
Lytés/BUN/Cr	X	X		X	X	X
LFT	X	X		X	X	X
Glucose	X					X
β-HCG ⁹	X					X
HIV/ID profile ⁶	X					X ⁸
Staging Scans ²	X				X	X
Immune ³	X	X		X	X	X ³
Biopsy		X ⁴		X ⁵		X ⁴
CEA		X			X	X

* or later

1. Participants will be monitored before the first vaccine and every 3 months with a CEA level (1 tsp) for the first 3 years and then every 6-12 months for a total of 5 years. Restaging CT scans (chest, abdominal, pelvic CT) will be performed at 3 months (or sooner if clinically indicated) following completion of vaccine and then every 6 months for the first three years and then yearly to year 5. After 5 years imaging will be at the discretion of the treating physician.
2. Staging scans should be a chest, abdominal, and pelvic CT and must be obtained within three weeks (21 days) of tumor harvest.
3. Approximately 50 cc of blood on a monthly basis during vaccination and every 3 months after completing all vaccinations for two years.
4. Biopsies of vaccination reaction (vaccine #1) will be taken 2 days after administration.
5. Biopsies of vaccination reaction (vaccine #5) will be taken 2 days after administration.
6. Testing for Infectious Disease Markers (IDM testing) should be performed within seven days of liver resection. IDM testing requires: Syphilis, CMV, HepBSAg, Hep B Core, HCV, HIV ½, HTLV ½, WNV.
7. Repeat if Tumor Harvest is required for second round of vaccine.
8. Serum pregnancy tests only required of women of childbearing potential
9. Vital signs are to be recorded 20-30 minutes after vaccine administration.

10. MEASUREMENT of EFFECT

Although response is not the primary endpoint of this trial, participants with measurable and/or non-measurable disease will be assessed by RECIST criteria. Restaging CT scans (chest, abdominal, pelvic CT) will be performed 3 months (or sooner if clinically indicated) following completion of vaccine and then every 6 months for the first three years and then yearly to year 5. After 5 years imaging will be at the discretion of the treating physician. In addition to a baseline scan, confirmatory scans should also be obtained twelve weeks following initial documentation of an objective response

10.1 Antitumor Effect– Solid Tumors

Restaging CT scans (chest, abdominal, pelvic CT) will be performed 3 months (or sooner if clinically indicated) following completion of vaccine and then every 6 months for the first three years and then yearly to year 5. After 5 years imaging will be at the discretion of the treating physician. In addition to a baseline scan, confirmatory scans should also be obtained every 12 weeks following initial documentation of objective response.

Response and progression will be evaluated in this study using the new international criteria proposed by the Response Evaluation Criteria in Solid Tumors (RECIST) guideline. Changes in the diameter (unidimensional measurement) of the tumor lesions are used in the RECIST criteria

Definitions

Evaluable for toxicity. All participants who receive at least one dose of study treatment will be evaluable for toxicity from the time of their first treatment.

Evaluable for objective response. Only those participants who have measurable disease present at baseline, have received at least one cycle of therapy, and have had their disease re-evaluated will be considered evaluable for response. These participants will have their response classified according to the definitions stated below. (Note: Participants who exhibit objective disease progression or die prior to the end of the first 6 vaccines will also be considered evaluable.)

10.1.1 Disease Parameters

Measurable disease.

Measurable disease is the presence of at least one (1) lesion that can be accurately measured in at least one dimension with longest diameter ≥ 20 millimeters (mm) using conventional techniques (CT, MRI, x-ray) or ≥ 10 mm with spiral CT scan. Measurable lesions must be at least 2 times the slice thickness in mm. All tumor measurements must be recorded in millimeters (or decimal fractions of centimeters).

Malignant lymph nodes. To be considered pathologically enlarged and measurable, a lymph node must be ≥ 15 mm in short axis when assessed by CT scan (CT scan slice thickness recommended to be no greater than 5 mm). At baseline and in follow-up, only the short axis will be measured and followed

Non-measurable disease.

All other lesions (or sites of disease), including small lesions (longest diameter <20 mm with conventional techniques or <10 mm using spiral CT scan), are considered non-measurable disease. Bone lesions, leptomeningeal disease, ascites, pleural/pericardial effusions, lymphangitis cutis/pulmonis, inflammatory breast disease, abdominal masses identified by physical exam that are not measurable by reproducible imaging techniques, and cystic lesions are all considered non-measurable.

10.1.2 Methods for Evaluation of Measurable Disease

All measurements should be taken and recorded in metric notation, using a ruler, calipers, or digital measurement tool. All baseline evaluations should be performed as closely as possible to the beginning of treatment and never more than 4 weeks before the beginning of the treatment.

The same method of assessment and the same technique should be used to characterize each identified and reported lesion at baseline and during follow-up. Imaging-based evaluation is preferred to evaluation by clinical examination when both methods have been used to assess the anti-tumor effect of a treatment.

Clinical lesions. Clinical lesions will only be considered measurable when they are superficial (e.g., skin nodules and palpable lymph nodes). For the case of skin lesions, documentation by color photography, including a ruler to estimate the size of the lesion, is recommended.

Chest x-ray. Lesions on chest x-ray are acceptable as measurable lesions when they are clearly defined and surrounded by aerated lung; however, CT is preferable.

Conventional CT and MRI. These techniques should be performed with cuts of 10 mm or less in slice thickness contiguously. Spiral CT should be performed using a 5 mm contiguous reconstruction algorithm. This applies to tumors of the chest, abdomen, and pelvis. Head and neck tumors and those of extremities usually require specific protocols.

Ultrasound (US). When the primary endpoint of the study is objective response evaluation, US should not be used to measure tumor lesions. It is, however, a possible alternative to clinical measurements of superficial palpable lymph nodes, subcutaneous lesions, and thyroid nodules. US might also be useful to confirm the complete disappearance of superficial lesions usually assessed by clinical examination.

FDG PET and PET/CT. The acquisition of FDG PET and FDG PET/CT scans should follow the NCI Guidelines for using FDG PET as an indicator of

therapeutic response {Shankar, 2006 #3452}, Patients should avoid strenuous exercise and be on a low carbohydrate diet for 24 hours prior to the scan. Patients should fast for 4 hours or longer prior to the FDG injection and should have a serum glucose of less than 200 mg/dL at the time of FDG injection. A 10-20 mCi dose of FDG should be injected for typical adult patients. For longitudinal studies with multiple scans, particular attention should be paid to ensure consistent patient preparation and acquisition parameters between the follow-up scan and the baseline scan. When designing a study where PET scans are going to be utilized as one of the modalities to evaluate efficacy, it is important to consult with physicians in nuclear medicine in designing the appropriate criteria to be utilized.

Tumor markers. Tumor markers alone cannot be used to assess response. If markers are initially above the upper normal limit, they must normalize for a subject to be considered in complete clinical response. Specific additional criteria for standardized usage of prostate-specific antigen (PSA) and CA-125 response in support of clinical trials are being developed.

Cytology, Histology. These techniques can be used to differentiate between partial responses (PR) and complete responses (CR) in rare cases (e.g., residual lesions in tumor types, such as germ cell tumors, where known residual benign tumors can remain).

The cytological confirmation of the neoplastic origin of any effusion that appears or worsens during treatment when the measurable tumor has met criteria for response or stable disease is mandatory to differentiate between response or stable disease (an effusion may be a side effect of the treatment) and progressive disease.

10.1.3 Response Criteria

10.1.3.1 Evaluation of Target Lesions

Complete Response (CR):

Disappearance of all target lesions. Any pathological lymph node must have reduction in short axis to < 10 mm.

Partial Response (PR):

At least a 30% decrease in the sum of the diameters of target lesions, taking as reference the baseline sum diameters.

Progressive Disease (PD):

At least a 20% increase in the sum of the diameters of target lesions, taking as reference the smallest sum on study with at least a 5

mm absolute increase in the sum of all lesions. The appearance of one or more new lesions* denotes disease progression.

Stable Disease (SD):

Neither sufficient shrinkage to qualify for PR nor sufficient increase to qualify for PD, taking as reference the smallest sum diameters while on study.

Unknown (UN): Assessment of target lesions cannot be made due to insufficient or unevaluable data. In this case, a concise explanation must be given.

Note: If tumor response data is missing for target lesions, the overall assessment must be UN unless there is new disease that would result in an overall assessment of PD. However, if there is missing or unevaluable data for non-target lesions, but data is available for all target lesions, the overall response for that time point will be assigned based on the sum LD of all target lesions. Additionally, the assessment of CR cannot be made if there is missing or unevaluable data for non-target lesions. In this case, the overall assessment would be PR.

***Definition of New Lesion:** The finding of a new lesion should be unequivocal (i.e. not due to difference in scanning technique, imaging modality, or findings thought to represent something other than tumor (ex: new bone lesions may be healing or flare of pre-existing lesions). However, a lesion identified on a follow-up scan in an anatomical location that was not scanned at baseline is considered new and will indicate PD. If a new lesion is equivocal (because of small size, etc.), follow-up evaluation will clarify if it truly represents new disease and if PD is confirmed, progression should be declared using the date of the initial scan on which the lesion was discovered.

10.1.3.2 Evaluation of Best Overall Response

The best overall response is the best response recorded from the start of the treatment until disease progression/recurrence (taking as reference for progressive disease the smallest measurements recorded since the treatment started). The participant's best response assignment will depend on the achievement of both measurement and confirmation criteria.

For Patients with Measurable Disease (i.e., Target Disease)

Target Lesions	Non-Target Lesions	New Lesions	Overall Response	Best Overall Response for when Confirmation is Required:
CR	CR	No	CR	≥ 4 wks confirmation
CR	Non-CR/Non-PD	No	PR	
CR	Not evaluated	No	PR	
PR	Non-CR/Non-PD/Not evaluated	No	PR	
SD	Non-CR/Non-PD/Not evaluated	No	SD	Documented at least once ≥ 4 wks from baseline
PD	Any	Yes or No	PD	
Any	PD*	Yes or No	PD	
Any	Any	Yes	PD	

* In exceptional circumstances, unequivocal progression in non-target lesions may be accepted as disease progression.
 
Note: Participants with a global deterioration of health status requiring discontinuation of treatment without objective evidence of disease progression at that time should be reported as "symptomatic deterioration". Every effort should be made to document the objective progression even after discontinuation of treatment.
				

For Patients with Non-Measurable Disease (i.e., Non-Target Disease)

Non-Target Lesions	New Lesions	Overall Response
CR	No	CR
Non-CR/non-PD	No	NonCR/non-PD
Not all evaluated	No	Not evaluated
Unequivocal PD	Yes or No	PD
Any	Yes	PD

Non-CR/non-PD is preferred over stable disease for non-target disease since SD is increasingly used an endpoint for assessment of efficacy in some trials so to assign this category when no lesions can be measured is not advised.
		

10.1.4 Duration of Response

Duration of overall response: The duration of overall response is measured from the time of operation until the first date that recurrence is objectively documented or death.

Duration of overall complete response: The duration of overall CR is measured from the time measurement criteria are first met for CR until the first date that recurrent disease is objectively documented.

Duration of stable disease: Stable disease is measured from the start of the treatment until the criteria for progression are met, taking as reference the smallest measurements recorded since the treatment started.

10.1.5 Progression-Free Survival

Progression-Free Survival (PFS) is defined as the length of time during and after the treatment of a cancer, that a patient lives with the disease but it does not get worse, as per the NCI. For this clinical trial it is measured as the duration of time between the hepatic resection to the time of objective disease progression (recurrence) or death.

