1.3 Secondary Objectives

- 1.3.1 To determine the progression free survival and two-year survival of stage IV colorectal cancer patients vaccinated with lethally irradiated, autologous colorectal cancer cells engineered by adenoviral mediated gene transfer to secrete GM-CSF.
- 1.3.2 To evaluate the immune response elicited by the vaccine.

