5.1.2 Vaccine administration

Treatment will be administered on an outpatient basis. It is expected that patients will have fully recovered from surgery and chemotherapy prior to administration of vaccine, per treating surgeon. In addition, patients may receive postoperative chemotherapy at the discretion of the treatment team. Treatment with GVAX may not start prior to 4 weeks after the last dose of chemotherapy or the operation. GVAX treatment must begin within 6 months of the date of operation. If enough vaccine is made patients may elect to have an additional 6 vaccines if they still meet the eligibility criteria.

Following notification by the treating provider that vaccine may be administered, the CMCF staff will be notified to thaw the vaccine. Vaccines will be retrieved from the CMCF by an authorized study team member as noted, according to CMCF policy and brought to the MGH on ice via the Partners shuttle or in a taxi between 1-4 hours prior to vaccine administration. The vaccine will be stored on ice until it is ready to be administered.

Expected toxicities and potential risks as well as dose modifications for GVAX are described in Section 6 (Expected Toxicities and Dosing Delays/Dose Modification). No

investigational or commercial agents or therapies other than those described below may be administered with the intent to treat the participant's malignancy.

Vaccination Plan					
Agent	Pre-medications; Precautions	Range	Route	Schedule	Cycle Length
GVAX	No premedications	1x10 ⁵ to 1x10 ⁷ cells/vaccine	Subcutaneous and Intradermal	Days 1,8,15, 29,43, 57	57 days

5.1.2.1 Vaccinations will be administered on days 1, 8, 15, and every two weeks thereafter until 6 vaccines have been administered or the patient is removed from study. As indicated in 5.2.2.4, individual vaccine cell dose will vary depending on the final cell yield from vaccine production. The total cell yield will be divided in 6 equal aliquots, and the minimal dose will be 1x10⁵ cells/vaccine and maximal dose will be 1x10⁷ cells/vaccine. This variation in cell dosage is designed to maximize each patient's opportunity of receiving vaccinations and is not based on any expectation of significant differences in toxicity as a function of cell number.

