5.1.2.2 All patients receiving at least one vaccination will be evaluable for toxicity. Patients will be considered evaluable for biologic activity if at least six vaccinations have been administered at a given dose level. There is no requirement for a particular number of patients at each cell dose level.

5.1.2.3 Vaccinations may be administered within 24 hours of the scheduled vaccine administration date (e.g. day 8, 15, 29) beginning with the day 8 vaccine.

5.1.2.4 Patients must be greater than 28 days from any chemotherapy, radiotherapy, immunotherapy, systemic glucocorticoid therapy, or resection of hepatic colorectal metastasis.

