5.2 Pre-treatment Criteria

5.2.1 Primary Tumor Procurement

5.2.1.1 Patients will undergo a surgical procedure (hepatic resection) to obtain tissue for vaccine preparation.

5.2.1.2 The responsible surgeon will send a portion of the tumor for standard of care pathology review. Then, the surgeon will place the research tumor specimen in sterile media in a sterile container. After gross evaluation by the pathologist of

the entire specimen in the operating room, the tissue will be transferred to the authorized study team member for vaccine processing at the DFCI CMCF.

5.2.1.3 Patients will receive routine post-operative care.

5.2.1.4 At the discretion of the treating physician patients may receive post operative chemotherapy prior to vaccine administration. Participants will undergo a separate standard of care chemotherapy consent session with their treating physician as the chemotherapy is not a part of the investigational agent in this study.

5.2.1.5 If recurrent disease is identified on the restaging scans prior to vaccine, vaccine will not be administered.

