14.1 Study Design/Endpoints

Primary

- 14.1.1 To determine the feasibility of manufacturing lethally irradiated, autologous colorectal cancer cells engineered by adenoviral mediated gene transfer to secrete GM-CSF from hepatic metastases.
- 14.1.2 To determine the safety and biologic activity of vaccination with lethally irradiated, autologous colorectal cancer cells engineered by adenoviral mediated gene transfer to secrete GM-CSF in stage IV colorectal cancer patients.

Secondary

- 14.1.3 To determine the progression free survival and two-year survival of stage IV colorectal cancer patients vaccinated with lethally irradiated, autologous colorectal cancer cells engineered by adenoviral mediated gene transfer to secrete GM-CSF

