14.3 Reporting and Exclusions

- 14.3.1 **Feasibility**- Feasibility will be defined by the capacity for patients in this specific population to initiate the vaccination process, i.e., to receive at least one vaccination. This will be governed by the ability to successfully harvest a minimum number of viable tumor cells at the time of surgery.

At the treating physician's discretion, patients with progressive disease or treatment-related complications between surgery and initiation of vaccination who are deemed incapable of or inappropriate for treatment will not initiate vaccination and will be included in the feasibility analysis.

We will consider this treatment plan feasible in this patient population if at

least 60% of initially enrolled patients go on to begin vaccination.

If an enrolled patient withdraws from the study for a reason that is not associated with surgical morbidity or disease progression, that patient will not be counted in the feasibility analysis.

14.3.2 **Safety and Biologic Activity:** All participants who receive at least one vaccine will be considered evaluable for toxicity. All participants who receive all 6 vaccines will be evaluable for biologic response.

14.3.3 **Evaluation of response.** All participants included in the study must be assessed for response to treatment, even if there are major protocol treatment deviations or if they are ineligible. Each participant should be assigned one of the following categories: 1) complete response, 2) partial response, 3) stable disease, 4) progressive disease, 5) early death from malignant disease, 6) early death from toxicity, 7) early death because of other cause, or 9) unknown (not assessable, insufficient data). By arbitrary convention, category 9 usually designates the "unknown" status of any type of data in a clinical database.

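### PFS is timed from hepatic resection but described for vaccinated patients, and no PFS analysis set is named; if the set is the vaccinated, the time before first vaccination is guaranteed free of identified events

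*Combined protocol and SAP*

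**What the plan says.** - **Origin.** In section 10.1.5, for this trial, "it is measured as the duration of time between the hepatic resection to the time of objective disease progression (recurrence) or death". The section does not say which patients are analysed.
- **Population.** Objective 1.3.1 reads "To determine the progression free survival and two-year survival of stage IV colorectal cancer patients vaccinated with lethally irradiated", and the secondary endpoint in 14.1.3 repeats it: "progression free survival and two-year survival of stage IV colorectal cancer patients vaccinated with lethally irradiated". Neither gives an origin for two-year survival.
- **Gap before vaccination.** Section 5.1.2.4 sets the minimum: "Patients must be greater than 28 days from any chemotherapy, radiotherapy, immunotherapy, systemic glucocorticoid therapy, or resection of hepatic colorectal metastasis". Section 5.1.2 sets the maximum: "GVAX treatment must begin within 6 months of the date of operation". Postoperative chemotherapy may be given in between.
- **Condition for vaccination.** Section 5.2.1.5: "If recurrent disease is identified on the restaging scans prior to vaccine, vaccine will not be administered". Exclusion 3.2.8 also rules out residual or recurrent disease.
- **Patients who never start.** Section 14.3.1 foresees "patients with progressive disease or treatment-related complications between surgery and initiation of vaccination". Those judged unable or unsuitable, at the treating physician's discretion, do not start and are counted in the feasibility analysis.
- **Analysis sets.** Section 14.3 says who counts for feasibility, toxicity, biologic activity and response. It has no entry for PFS.

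**The concern.** A patient joins the vaccinated group only by being alive, with no recurrence identified, when the first vaccine is due. If PFS in that group is counted from the operation, the interval before vaccination adds progression-free time that entry to the group guaranteed. Patients with an identified recurrence, or a death, in the same interval drop out of the group and contribute no event. This is guaranteed (immortal) time. It lengthens PFS even if the vaccine does nothing, it always acts in the same direction, and it does not shrink with more patients.

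What is at stake is how a descriptive secondary estimate is read. The curve would look too favourable if taken as the PFS of resected patients, for example beside an outside resection series. Two-year survival raises the same question, since its population is also the vaccinated and its origin is unstated.

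**Working it through.** **The plan's own figures.** None concerns PFS: there is no stated median, rate, event count or power for it. The figures in section 14 do reproduce by exact binomial calculation with 15 patients. The rule of at least 9 successes gives one-sided alpha 0.1818 at 45% (stated 0.18) and power 0.7548 at 65% (stated 75%). The safety rule of 3 or more gives 0.0362 at a rate of 0.05 and 0.7639 at 0.25 (stated 0.04 and 0.76). None depends on the PFS definition.

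**Inputs for the bias.**
- From the documents: gap L from resection to first vaccination of 28 days (28/30.4 = 0.92 month) up to 6 months; at most 15 patients.
- Assumed: exponential PFS from resection with median m = 12, 18 or 24 months; an inert vaccine; all patients starting at the same L; a share d of pre-vaccine events identified, so that those patients are not vaccinated.

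**All pre-vaccine events identified (d = 1).** In all resected patients S(24) = 2^(−24/m). In vaccinated patients timed from resection it becomes S(24)/S(L) = 2^(−(24−L)/m).

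| m (months) | All resected | Vaccinated, L = 0.92 | Vaccinated, L = 6 |
|---|---|---|---|
| 12 | 25.0% | 26.4% (+1.4) | 35.4% (+10.4) |
| 18 | 39.7% | 41.1% (+1.4) | 50.0% (+10.3) |
| 24 | 50.0% | 51.3% (+1.3) | 59.5% (+9.5) |

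Example, m = 12 and L = 6: 2^(−18/12) = 0.354, against 2^(−24/12) = 0.250.

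**Incomplete identification.** The bar in 5.2.1.5 acts only on recurrence that is found. The vaccinated-group figure is then S(24)/(1 − d(1 − S(L))). With d = 0.5, m = 12 and L = 6: S(6) = 0.707, the denominator is 1 − 0.5 × 0.293 = 0.854, and 0.250/0.854 = 0.293, or +4.3 points. For m = 18 and 24 the excess is +4.6 and +4.3. At L = 0.92 it is +0.7 for all three medians.

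**Random error for comparison.** The 95% half-width is 1.96 × √(p(1−p)/n). With n = 15 it is 21.9, 24.8 and 25.3 points at p = 0.25, 0.40 and 0.50. Section 14.3.1 calls the plan feasible if at least "60% of initially enrolled patients go on to begin vaccination". With 0.60 × 15 = 9 patients the half-widths are 28.3, 32.0 and 32.7 points.

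**Do the remedies work?** A simulation of 20,000 patients used planned starts spread uniformly over 0.92 to 6 months and d = 1.

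| m (months) | From resection | Delayed entry (target) | From first vaccination (target) |
|---|---|---|---|
| 12 | 30.4% | 26.3% (26.4%) | 24.9% (25.0%) |
| 24 | 55.4% | 51.6% (51.3%) | 50.3% (50.0%) |

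Delayed entry targets PFS given event-free at about 28 days. The match for first-vaccination timing follows from the memoryless exponential and is not independent evidence. Under a falling hazard, the selection of patients who stayed recurrence-free would remain.

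**The case against.** The strongest reply is that no mismatch is established, because no passage fixes the PFS set. Objectives 1.3.1 and 14.1.3 may simply describe the treatment under study. Patients are screened before the operation, and resection is a step of the treatment plan. Section 14.3.3 requires every participant to be assessed, with categories for progression and early death. Resection would be a sound origin for all enrolled, resected patients. It stands that the set is unnamed, so the point is conditional. But 14.3.3 governs response categories and sets neither a PFS population nor an origin, and the only wording attached to PFS speaks of the vaccinated.

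Three further points limit the concern:

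- A reader might infer that nothing is assessed before vaccination. That is not so. Section 5.2.1.5 refers to restaging scans before vaccine, the study calendar has CEA before the first vaccine, and 10.1.2 asks for baseline evaluation within 4 weeks before treatment. What is not scheduled (5.6, the calendar, 10.1) is later follow-up of patients who are never vaccinated.
- A reader might take 6 months as the usual gap. It is only the upper limit in 5.1.2. Exclusion 3.2.10 rules out patients more than one month from the resection that supplies the vaccine. If that governs first vaccination, the gap is about a month and the bias small. The two passages must be reconciled.
- A reader might infer that no vaccinated patient could have recurred before vaccination. Undetected recurrence is possible, and 14.3.1 leaves some non-initiation to physician discretion, whereas 5.2.1.5 is categorical.

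**Conclusion.** The point holds in conditional form. If PFS is analysed in vaccinated patients, as 1.3.1 and 14.1.3 word it, timing it from resection credits each patient with pre-vaccine time in which no death and no identified recurrence could occur. That follows from the text and needs no assumed figure.

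The size does rest on assumptions: an exponential median of 12 to 24 months, an inert vaccine and a common start time. On these, 24-month PFS is overstated by between 0.7 points (28-day gap, half identified) and 10.4 points (6-month gap, all identified). The actual gaps and the share identified are unknown.

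Severity is low. The estimate is secondary and descriptive, the section on statistics sets no PFS benchmark, and the bias lies inside the random error. A reader might infer that the trial's decision rules or its case for a later study are compromised. The documents do not support this: the feasibility and safety rules do not use PFS, and section 1.1 makes a later study depend on biologic activity without substantive toxicity.

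**What to change.** In 10.1.5 and 14.1.3:

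1. Name the PFS set as patients who receive at least one vaccination.
2. Either start PFS at first vaccination (Day 1), or keep resection as the origin with delayed entry at first vaccination. Delayed entry estimates PFS given event-free at about 28 days and will have small early risk sets with at most 15 patients.
3. State the origin of two-year survival in the same way.
4. Report the distribution of the resection-to-first-vaccination interval.
5. State that Day 1 timing removes the guaranteed time but not the selection of patients who stayed recurrence-free, so comparison with outside figures remains limited.

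Separately, reconcile exclusion 3.2.10 with the window in 5.1.2, since the size of the bias depends on that gap.

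PFS from resection in all enrolled, resected patients is an acceptable alternative only if pre-vaccine recurrences and deaths count as events, and never-vaccinated patients are either followed or censored with the reason reported.

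**Cost.** The main fix takes a few sentences and needs only the dates of resection and first vaccination. The reported PFS of vaccinated patients becomes shorter. The all-enrolled alternative costs more: it needs follow-up of never-vaccinated patients that the plan does not now schedule, or acceptance of their censoring.
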